3.1.3 Intercurrent Events

The following intercurrent events will be handled using a treatment policy strategy. That is, the primary endpoint will be defined to be the earliest of the time to relapse as described in Section 8.1 and the time at which any of the events defined below occur.

Table 6 Intercurrent Events and the Statistical Treatment

Permanent discontinuation of study medication unrelated to treatment.	Censored
Permanent discontinuation of study medication related to treatment.	Estimand event
Temporary discontinuation of study medication regardless of relationship to treatment will be discussed by the Sponsor and the Investigator to determine whether patient can stay in the study and restart treatment (see Section 7.1.1).	In case of permanent discontinuation, see rows 1 and 2.
Initiation of treatment with any systemic CCSs (not related to AIH), or any other prohibited concomitant medication listed in Section 6.5.2.	Censored
Death due to any cause.	Censored
Liver transplant.	Censored
CCS increase during tapering or reintroduction related to AIH.	Estimand event

In the primary analysis of the primary estimand, participants who experience any of these intercurrent events will have a response status as indicated in Table 6 at the time of their earliest intercurrent event. Other strategies will be adopted in sensitivity analyses (see Section 3.1.5).

Participants who neither relapse nor experience any of the intercurrent events will be regarded as censored on the date of their last known follow-up.

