7.1 DISCONTINUATION OF STUDY TREATMENT

For data to be collected at the time of treatment discontinuation and follow-up and for any further evaluations that need to be completed see the SoA (Section [1.3](#)).

Reasons for discontinuation of study treatment (or withdrawal from the study) may include, but are not limited to, the following:

- Participant withdrawal of consent at any time.
- Any medical condition that the Investigator or Sponsor determines may jeopardize the participant's safety if he or she continues in the study.
- Investigator or Sponsor determination that treatment discontinuation is in the best interest of the participant.
- Pregnancy.
- Disease relapse (See Section [8.1](#)).
- Any event that meets stopping criteria defined in Section [4.1.3](#).

Every effort should be made to obtain information on participants who withdraw from the study but have not withdrawn consent. Participants who discontinue study treatment prematurely will be asked to return to the clinic for a study completion/early termination visit (see Section [8.11.3](#)) and may undergo follow-up assessments (see Section [8.11.4](#)), unless the participant withdrew consent. The primary reason for premature study treatment discontinuation should be documented on the appropriate eCRF. Participants who discontinue study treatment prematurely will not be replaced.

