8.1 EFFICACY ASSESSMENTS

The primary efficacy endpoint of this study is time from randomization to relapse. Relapse is defined in Table 8. ALT and IgG will be assessed centrally according to the SoA (see Section 1.3). If a value exceeds the defined threshold, the site will be notified immediately, and a confirmatory sample will be taken no less than 7 days after the sample showing exceeding the threshold the first time. If the values returned to below the threshold in the repeat measurement, the participant can continue in the study. If the values still exceed the threshold, the participant can be either re-tested (as described in Table 8) or will be counted as having a relapse and leave the study, depending on the test results. SoC should be started as soon as relapse is confirmed.

If CCSs are increased during tapering or re-introduced because of AIH flare as per Investigator assessment (e.g., ALT > 1 and < 2 for extended period or biopsy finding), the incidence will be counted as an event, and the respective participant should stop study treatment.

Changes in ALT, AST, and IgG will be assessed according to the SoA (Section 1.3).

Table 8 Decision Tree for ALT or IgG Increase

ALT $\geq 2 \times$ ULN < $5 \times$ ULN	Confirm +7 days	
 – If < $2 \times$ ULN \rightarrow return to normal schedule – If $\geq 2 \times$ ULN and < $3 \times$ ULN \rightarrow retest + 7 days \rightarrow if not < $2 \times$ ULN = relapse: end of study – If $\geq 3 \times$ ULN \rightarrow relapse: end of study
ALT $\geq 5 \times$ ULN	Relapse: end of study	
IgG > $1 \times$ ULN < $1.5 \times$ ULN	Confirm +14 days	
 – If $\leq 1 \times$ ULN \rightarrow return to normal schedule – If > $1 \times$ ULN and < $1.5 \times$ ULN \rightarrow retest + 14 days; if > $1 \times$ ULN \rightarrow relapse: end of study – If $\geq 1.5 \times$ ULN \rightarrow relapse; end of study
IgG $\geq 1.5 \times$ ULN	Relapse: end of study	

Study treatment continues as per SoA (see Section 1.3) until relapse criteria are met.

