8.11.3 Assessments at Study Completion/Early Termination Visit

Participants who complete the study (defined as relapse) or discontinue from the study early will be asked to return to the clinic 28 days \pm 3 days after the final dose of study treatment for a follow-up visit.

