9. STATISTICAL CONSIDERATIONS

9.1 STATISTICAL HYPOTHESES

The hypothesis associated with the primary estimand (see Section 3.1) for this study is that the hazard ratio (HR) for the risk of relapse in the 7.5 mg RO7049665 compared with that of placebo is less than 1. In other words, that 7.5 mg RO7049665 increases the time to relapse following forced tapering of CCS/ \pm NSI therapy in participants with confirmed AIH who have been in stable biochemical remission for at least two years (*or less if according to the local practice*) and on stable AIH treatment for *at least 3 months prior to randomization (and who have not had a dose increase 6 months prior to randomization)*.

Six months after the start of CCS tapering, the relapse rate on placebo is assumed to be 45% (van Gerven 2013). It is estimated that treatment with RO7049665 will reduce the relapse rate to 15%. Under the assumption of exponential times to relapse, these six-month relapse rates imply mean times to relapse of 10.0 months in the placebo arm and 36.9 months in the treatment arm, leading to a reference hazard ratio of 0.272.

The hypotheses formally tested in this study are

$$H_0: HR = 1 \text{ vs } H_1: HR < 1$$

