9.2 SAMPLE SIZE DETERMINATION

The sample size for this study is based on independent pairwise comparisons of each RO7049665 group—i.e., high dose (7.5 mg) and low dose (3.5 mg) with placebo. The total sample size required is obtained by multiplying the appropriate per-group size by three. Methods for the control of the family-wise error rate are described both in this section and in Section 9.3.

The reference treatment effect is 0.272. The study will use an overall one-sided type 1 error rate (significance level) of 2.5%. A power of 90% against the reference treatment effect is required.

There will be one opportunity to stop for success before the end of the study, at 50% information. An O'Brien-Fleming-like alpha-spending rule will preserve the type 1 error rate. The success boundary will be binding.

There will be two opportunities to stop for futility before the end of the study: once at 25% information (i.e., when 25% of the maximum number of events have occurred) and once at 50% information (i.e. when 50% of the maximum number of events have occurred). A Pocock-like beta-spending rule will preserve power of the study. The futility boundary will be non-binding.

If the proportional hazards assumption holds, these assumptions imply that 29.1 events (i.e., 30 events for all practical purposes) in the placebo and 7.5 mg RO7049665 arms combined are required to achieve the desired power and significance levels.

Under the assumption that recruitment to the study will take approximately 19 months, that sites will be activated at uniform rate for six months, after which recruitment will plateau, and that follow-up should continue for at most 6 months after the last patient to enter the study is randomized, then recruitment of 28 participants per arm will generate the required number of events.

Table 9 Summary of the Group Sequential Design

Stage	Interim 1	Interim 2	End of study
Information rate	25%	50%	100%
Efficacy boundary (z-value scale)	∞	2.963	1.969
Futility boundary (z-value scale)	-0.046	0.738	
Number of subjects ^{a,c}	31	47	56
Cumulative number of events ^a	7.3	14.5	29.1
Analysis time ^{b,c}	11.7	16.3	25.0
Cumulative alpha spent	<0.0001	0.0015	0.025
Cumulative power	<0.0001	0.3159	0.9000
One-sided local significance level	N/A	0.0015	0.0245 ^d
Efficacy boundary (t)	N/A	0.211	0.482
Futility boundary (t)	1.035	0.679	
Overall exit probability (under H0)	0.4815	0.3136	
Exit probability for efficacy (under H0)	<0.0001	0.0015	

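### Sections 3.1.3 and 8.1 can score the same AIH flare differently: if study drug is stopped first, the flare may be censored instead of counted

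*Combined protocol and SAP*

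**What the plan says.** Section 3.1.3 names a treatment policy strategy. It then defines the endpoint as the earlier of relapse under Section 8.1 and any listed intercurrent event. A participant with such an event "will have a response status as indicated in Table 6 at the time of their earliest intercurrent event". In Table 6:

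- Row 1, "Permanent discontinuation of study medication unrelated to treatment": censored.
- Row 2, a permanent stop related to treatment: event. Related is not defined.
- Row 3, a temporary interruption that becomes permanent: referred to rows 1 and 2, with no date given.
- Last row, CCS increased during tapering or reintroduced for AIH: event.

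Section 8.1 says of CCS raised or restarted for an investigator-assessed flare that "the incidence will be counted as an event, and the respective participant should stop study treatment". It sets no condition on what happened before.

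Section 7.1 lists, separately from relapse, "Investigator or Sponsor determination that treatment discontinuation is in the best interest of the participant" as a reason to stop drug. Section 4.1.3 also allows a discretionary stop.

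Section 3.1.2 dates a confirmed relapse to the first set of abnormal tests. Under Section 8.11.3, participants who relapse or "discontinue from the study early will be asked to return to the clinic 28 days", plus or minus 3, after the final dose. Table 1 schedules blood chemistry at the early-termination and follow-up visits, and Appendix 4 includes ALT and IgG in that panel.

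**The concern.** Event status in the primary analysis can turn on the order of two dates and on an undefined label. A participant taken off drug because a flare is developing is more likely than others to relapse, so censoring at the stop is informative. A relapse first seen on ALT or IgG after a stop classed as unrelated does not count either, although the samples are scheduled. Under a treatment policy strategy, outcomes seen after the intercurrent event would be used; Table 6 ends observation at that event.

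The primary comparison needs only about 29 events, so a few reclassified flares matter. Equal loss across arms costs events. Unequal loss biases the hazard ratio.

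**Working it through.** **Order of events.** Days 100 and 103 are illustrative.

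| Sequence | Section 8.1 | Primary analysis, Section 3.1.3 |
|---|---|---|
| A. First abnormal test before the stop and later confirmed, or a single ALT ≥ 5 × ULN or IgG ≥ 1.5 × ULN before the stop | Relapse | Event, dated at that test |
| B. CCS for AIH on day 100, drug stopped on day 103 | Event | Event, day 100 |
| C. Drug stopped on day 100 for a flare with no qualifying test; CCS for AIH or first threshold crossing on day 103 or later | Event | Censored at day 100 if unrelated; event if related |
| D. ALT 2 to < 5 × ULN, drug stopped, CCS started on a later day, relapse never confirmed | Event | Censored if unrelated; event if related |
| E. Stop and CCS on the same day | Event | Not determined |
| F. Interruption, relapse during the pause, then permanent stop | Relapse | If the stop is classed unrelated: event if dated at the decision, censored if dated at the last dose |

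B and C can be the same flare with the two dates reversed.

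**Sensitivity analyses (Section 3.1.5).** The first counts a triggering test whatever its confirmation shows, so it recovers D. Two others recode all intercurrent events as relapses (deaths and transplants included) or all as censored (CCS for AIH included). The fourth imputes missing laboratory values. None uses the status observed after the stop, which is what C needs.

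**The plan's own figure.** Section 9.1 gives 6-month relapse of 45% on placebo and 15% on active with exponential times, "leading to a reference hazard ratio of 0.272". Section 9.2 gives one-sided 2.5% error and 90% power.

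- Monthly hazards: −ln(0.55)/6 = 0.0996 and −ln(0.85)/6 = 0.0271; ratio 0.272.
- Fixed design (Schoenfeld): 4 × (1.960 + 1.282)² / (ln 0.272)² = 24.8 events.
- Group sequential inflation for the stated spending rules: 1.174, so 24.8 × 1.174 = 29.1 events, as stated. The boundaries 2.963 and 1.969, and −0.046 and 0.738, also match Table 9.
- With 28 per arm, a 6-month linear ramp, accrual to month 19 and analysis at month 25: 20.3 + 8.7 = 29.06 events.

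**Size of the loss.** The documents give no share, so m below is assumed. If a share m of an arm's relapses is censored at about the time each would have counted, the counted hazard is (1 − m) times the true one.

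| | m = 10% | m = 20% | m = 30% |
|---|---|---|---|
| Equal loss: events at month 25, (1 − m) × 29.06 | 26.2 | 23.2 | 20.3 |
| Equal loss: power at that cut, futility followed | 87.0% | 83.1% | 78.1% |
| Equal loss: placebo 6-month rate, 1 − exp(−6 × 0.0996 × (1 − m)) | 42% | 38% | 34% |
| Placebo-only loss: HR = 0.272/(1 − m) | 0.302 | 0.340 | 0.388 |
| Placebo-only loss: power at 29.1 events, futility followed | 85.0% | 77.4% | 66.3% |
| Active-only loss, true HR 1: observed HR = 1 − m | 0.90 | 0.80 | 0.70 |
| Active-only loss, true HR 1: one-sided type 1 error, futility not enforced | 4.7% | 8.7% | 15.9% |

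A single-look check of the last row: 1 − Φ(1.960 + ln(1 − m) × √29.1/2). At m = 10% this is 1 − Φ(1.960 − 0.284) = 4.7%.

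**The case against.** The best defence is that the normal sequence is already covered. Section 8.1 keeps dosing going until relapse criteria are met, counts CCS for a flare as an event, and only then has drug stopped. Section 4.1.3 describes relapse as study treatment failure, so a stop for flare could be read into row 2 and counted. The trial is event-driven, and Section 9.2 allows numbers or follow-up to be varied until the target is reached.

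Much of this stands. Censoring needs both an earlier stop date and the label unrelated, and nothing suggests that this sequence is common. With equal loss and extended follow-up the cost is time, not power, and the hazard ratio does not change. But reading a flare-driven stop into row 2 is a choice that the text neither makes nor excludes, and no rule settles C, E or F.

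A reader might infer three stronger things that the documents do not support:

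- That every flare is lost when drug stops before relapse is documented. Section 3.1.2 back-dates a confirmed relapse, so sequence A counts.
- That the end of monitoring about 28 days after the last dose causes the censoring. The earliest-event rule does so alone; the visit limit only prevents later relapses from being seen.
- That the drug's effect is necessarily understated, or that lost participants count as event-free to the cut-off. Loss on active biases the other way, and Table 6 removes participants from the risk set at the stop.

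**Conclusion.** The concern holds in a limited form. Sections 3.1.3 and 8.1 conflict for a flare in which drug is stopped before any qualifying test, the stop is labelled unrelated, and CCS or a threshold crossing follows on a later day. Such a flare is censored in the primary analysis, and no planned sensitivity analysis uses its observed outcome. Same-day events and interruptions that become permanent are left undetermined, and the treatment policy label does not describe what Table 6 does.

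Frequency and direction are unknown. The 10 to 30% shares are assumptions, and they also suppose that censoring falls close to when the relapse would have counted. Within that range the effect runs from lost time only, to an attenuated hazard ratio of about 0.30 to 0.39, to an inflated type 1 error of about 4.7 to 15.9%. The 29.1-event requirement is not in question. The rules should be settled before any unblinded interim look.

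**What to change.** Reconcile Sections 3.1.3 and 8.1, with the change made in 3.1.3:

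1. Define related to treatment, and say how a stop due to AIH flare or lack of efficacy is classified.
2. State that a Table 8 relapse, or CCS increased or reintroduced for AIH, seen up to the already scheduled 28-day follow-up visit takes precedence over row 1 censoring. Date it at the first qualifying test or the CCS start.
3. Add a same-day rule and a dating rule for interruptions that become permanent.
4. Censor participants with an unrelated stop and no such event at their last ALT/IgG assessment up to that visit, not at the stop. Otherwise post-stop time would enter only for those with events, and the hazard would be inflated.
5. Correct the treatment policy label, or add a supplementary analysis using all ALT/IgG observed after the stop.

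The cost is protocol and analysis wording; the samples are already scheduled. The downside is small: up to about 28 days of off-drug time enters the primary analysis. Sampling beyond that visit is an optional design choice and not part of this fix. The change concerns how events are classified and dated; it alters no dose, stopping rule or rescue rule.

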3.1.4 Summary Measure

The summary measure used to assess the effect of RO7049665 will be the hazard ratio for time to relapse between the relevant RO7049665 group and the SoC group, as

calculated by a Cox proportional hazards model with terms for treatment arm, sex, and prednisolone-equivalent CCS dose at baseline. If inclusion of any model term leads to model instability, then the terms included in the model may be modified.

3.1.5 Sensitivity Analyses

The most likely cause of “missing” confirmation of relapse is the absence of a confirmatory laboratory test results. Therefore, the first sensitivity analysis will define relapse to have occurred on the date of the tests that triggered the need for a subsequent confirmation, regardless of the result of that confirmation. The status of participants whose laboratory test results indicate definitive relapse without the need for confirmation will be unchanged. Moreover, if exactly one of the values for ALT or IgG is missing at a given visit, this analysis will assume that the missing test meets the criterion for retest, and therefore that the participant will have relapsed at that visit.

Additional sensitivity analyses will regard all intercurrent events listed above as relapses rather than as censorings and regard all intercurrent events listed above as censorings rather than as events.

The fourth and final sensitivity analysis will use multiple imputation to replace any missing laboratory test result with values selected at random from other participants in the study, matched for sex and prednisolone-equivalent CCS dose. Further details of the methodology used will be documented in the study electronic Trial Master File (eTMF).

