3.1.2 Endpoint

The patient-level endpoint that provides information about the question of scientific interest is the number of days from randomization to relapse. A participant will be considered to have relapsed the first time they meet the criteria given in Section 8.1 at a

post-baseline study visit, whether the visit is scheduled or unscheduled. If the relapse requires confirmation at a subsequent visit, the date of relapse will be the date of the first set of tests, if confirmed. The sensitivity analyses below will examine the effect of how missing confirmatory tests are handled and the impacts on the results of the trial.

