5.1 INCLUSION CRITERIA

Participants are eligible to be included in the study only if all of the following criteria apply:

Informed Consent

1. Able and willing to provide written informed consent and to comply with the study protocol according to International Conference on Harmonisation (ICH) and local regulations.

Age

2. Between 18 to 75 years of age, inclusive, at the time of signing the informed consent.

Type of Participants and Disease Characteristics

3. Patients with a definite diagnosis of AIH (type 1, 2 and 3) as per simplified or revised original diagnostic criteria (including response to CCSs) ([Hennes et al 2008](#)).
4. Patients who have been in biochemical remission (complete normalization of serum transaminases and IgG levels [*if IgG is measured, as according to local practice*]) for ≥ 2 years (*or less if according to the local practice*) prior to randomization. At least two measurements of IgG levels within normal range at least two weeks apart need to be available before randomization.
5. Patients who have been on stable treatment (CCSs \pm NSIs) for at least 3 months prior to randomization *and who have not had a dose increase in the previous 6 months prior to randomization*.
6. No signs of liver inflammation (HAI ≤ 3) on a liver biopsy taken no more than 12 months prior to randomization.
7. Patients with AIH who have previously not attempted (*or not attempted in the last 3 years, if this is the local practice*) to taper CCS to 0 mg/day.

Weight

8. Body mass index (BMI) within the range of 18-35 kg/m² (inclusive).

Sex and Contraception/Barrier Requirements

9. Male and female participants are eligible.

The contraception and abstinence requirements are intended to prevent exposure of an embryo to the study treatment. Therefore, the reliability of sexual abstinence for female enrollment eligibility needs to be evaluated in relation to the duration of the clinical study and the preferred and usual lifestyle of the participant. Periodic abstinence (e.g., calendar, ovulation, symptothermal, or post-ovulation methods) and withdrawal are not acceptable methods of preventing drug exposure.

A female participant is only eligible to participate if she is not pregnant, not breastfeeding, and at least one of the following conditions applies:

- Women of non-childbearing potential (WONCBP),

OR

- Women of childbearing potential (WOCBP), who:

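### Sensitivity analysis 1 is motivated by missing confirmatory tests but also recodes observed negative confirmations as relapses, so a difference from the primary hazard ratio cannot be attributed to missing tests

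*Combined protocol and SAP*

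**What the plan says.** All references are to the combined protocol and SAP.

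- **Purpose.** Section 3.1.2: "The sensitivity analyses below will examine the effect of how missing confirmatory tests are handled". Section 3.1.5 starts from the premise that the likeliest cause of missing "confirmation of relapse is the absence of a confirmatory laboratory test results".
- **Rule of analysis 1.** Section 3.1.5 then places relapse at the test that "triggered the need for a subsequent confirmation, regardless of the result of that confirmation". A second component treats a visit at which exactly one of ALT and IgG is missing as a relapse at that visit.
- **Primary rule.** Section 3.1.2: "the date of relapse will be the date of the first set of tests, if confirmed".
- **Negative repeats.** Section 8.1: "If the values returned to below the threshold in the repeat measurement, the participant can continue in the study". Table 8 sends such a participant to "return to normal schedule".
- **IgG trigger.** In Table 8 any IgG above 1 x ULN and below 1.5 x ULN leads to "Confirm +14 days". If the repeat is still in that band, a further retest is required before relapse is called. At entry, inclusion criterion 4 asks: "At least two measurements of IgG levels within normal range at least two weeks apart need to be available before randomization". Exclusion criterion 22 rules out IgG above normal.
- **Analysis 4.** Section 3.1.5 imputes missing laboratory values from other participants. The matching variables it states are sex and prednisolone-equivalent CCS dose, with further methodology left to the eTMF. Treatment arm and visit are not named.

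**The concern.** A confirmation that was obtained and came back negative is not missing. The primary analysis already dates a confirmed relapse at the triggering tests, so confirmed cases are identical under both definitions. What the trigger rule changes is (a) triggers with no confirmation and (b) triggers with an observed negative. If no confirmation is missing, it changes only (b), which is not the question that section 3.1.2 sets. The one-of-two-missing component adds a third source of difference to the same result.

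Negative repeats are foreseeable. Participants enter with IgG in the normal range, a single value just above 1 x ULN is a trigger, and relapse at values below 1.5 x ULN needs three consecutive values above 1 x ULN.

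At stake is the reading of a supportive analysis. A shifted HR could be taken as fragility to missing data when no data were missing, and an unshifted one as reassurance that it does not give. For analysis 4, donors drawn without regard to arm would carry no treatment effect into the imputed values, although arm is a term in the Cox model (section 3.1.4).

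**Working it through.** The central point follows from the text. The arithmetic below shows only how much the rule could matter.

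**1. The plan's own figures (sections 9.1 and 9.2).** Relapse at six months is 45% on placebo and 15% on 7.5 mg, with exponential times.
- Placebo hazard: -ln(0.55)/6 = 0.0996 per month, mean 10.0 months.
- 7.5 mg hazard: -ln(0.85)/6 = 0.0271 per month, mean 36.9 months.
- HR: 0.0271/0.0996 = 0.272, as stated.
- With 28 per arm, a six-month linear recruitment ramp, a plateau to month 19 and analysis at month 25, simulation gives 29.0 to 29.1 events. Table 9 has 29.1.

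**2. Who is recoded by the trigger rule.**

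| Repeat result | Primary | Analysis 1 |
|---|---|---|
| Confirms | Relapse at trigger date | Relapse at trigger date |
| Missing | Not confirmed | Relapse at trigger date |
| Observed negative | Not relapse, continues | Relapse at trigger date |

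Only the second row matches the stated reason.

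**3. Closed form, no confirmation missing.** Assume negative-repeat triggers at monthly rate q, equal in both arms. Then HR = (0.0271 + q)/(0.0996 + q).
- q = 0.01: 0.0371/0.1096 = 0.34
- q = 0.03: 0.0571/0.1296 = 0.44
- q = 0.05: 0.0771/0.1496 = 0.52

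A rule confined to missing confirmations stays at 0.272. If instead negative triggers are proportional to each arm's relapse hazard, HR = 0.0271(1 + k)/[0.0996(1 + k)] = 0.272 for every k, so there is no shift.

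**4. Per-draw simulation, no confirmation missing.** Assumed draws are weeks 2, 3, 4, 5, 7, 9, 11, 13, 17, 21 and 25, then every 4 weeks (the layout of Table 1 could not be read with certainty). All trigger rates are assumptions.

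| Negative-repeat triggers per draw | 0.5% | 1% | 2% |
|---|---|---|---|
| HR, equal in both arms | 0.32 | 0.37 | 0.45 |
| Negatives recoded, two arms | 3.9 | 7.4 | 13.7 |
| Events, two arms | 31.5 | 33.6 | 37.4 |
| HR, equal, 4-weekly draws throughout | 0.31 | 0.34 | 0.40 |
| HR, placebo only | 0.25 | 0.24 | 0.21 |
| HR, 7.5 mg only | 0.35 | 0.43 | 0.59 |

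Events rise by less than the number recoded because some recoded participants would have relapsed later.

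**5. Separating the two effects.** With 10% of confirmations missing in both arms, 12 months' follow-up and q = 0.01, 0.03 or 0.05 per month:
- confirmed relapses only: 0.29, 0.29, 0.29
- missing confirmations counted as relapse: 0.28, 0.29, 0.30
- all triggers counted: 0.34, 0.44, 0.52

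Here almost all of the movement comes from observed negatives.

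**6. Is 0.5% to 2% per draw reasonable?** It cannot be settled from the documents. With an assumed within-person IgG coefficient of variation of 5% (range 3% to 7%), a stable true level of 0.90 x ULN exceeds ULN on 1.3% of draws (0.01% to 5.6%). At 0.95 x ULN the figure is 14.6% (4.0% to 22.6%).

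**7. Analysis 4 with arm not used.** Assume 3.5 mg has the 7.5 mg hazard. The pooled hazard is (0.0996 + 2 x 0.0271)/3 = 0.0513. With a fraction m of results missing and one drawn value counting as relapse, HR = (0.0271 + 0.0513m)/(0.0996 + 0.0513m), which is 0.29, 0.31 and 0.34 for m = 5%, 10% and 20%. If Table 8 must be satisfied by the imputed values, simulation gives about 0.27 to 0.28.

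**The case against.** **The any-trigger rule is openly stated and is a fair bound.** It is a legitimate stress test of the confirmation requirement. What does not stand is offering it as the analysis of missing confirmations.

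**The missing-test question is covered elsewhere.** Section 3.1.2 speaks of the sensitivity analyses in the plural, and analysis 4 acts on missing laboratory values while leaving observed negatives alone. A reader might infer that the plan never addresses missing confirmations; the documents do not support that. Analysis 1 nevertheless remains uninterpretable on this question.

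**The size follows from the assumed rates.** This stands. The plan gives no trigger or missingness rate. The attenuation comes from assuming equal rates in both arms, and it vanishes under proportional rates. The simulation treats negative triggers as independent of later relapse; if they tend to precede it, recoding mainly moves dates. In the equal-rate cases the expected z, |ln HR| x sqrt(events/4), is 3.17, 2.88 and 2.45, still above the final boundary of 1.969, and no formal test rests on this analysis.

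**Opposite direction.** A reader might infer that analysis 1 moves the HR the opposite way from a missing-only rule. That can be constructed by letting 10% to 20% of confirmations be missing on placebo only, with those participants leaving and being censored. At 20% missing and 0.5% per draw it does not occur: the primary HR is 0.34, the missing-only rule gives 0.27 and analysis 1 gives 0.32. The plan would also recover some such cases, because steroid reintroduction for AIH is an event (Table 6) and early stoppers are asked back for a visit (section 7.1). The documents do not support a general claim.

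**Analysis 4 is not fully specified here.** A reader might infer that the imputation will ignore arm and visit. That does not follow, because the eTMF may add them. Section 3.1.5 also does not say that the matching dose is the baseline dose; if it is the current dose, matching would partly follow the taper.

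**Conclusion.** The mismatch is established from the text: the reason given for analysis 1 is missing confirmations, while its rule also recodes observed negatives and includes the one-of-two-missing rule. Its difference from the primary HR mixes these three sources and cannot be attributed to the first.

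The size is illustrative. Equal negative-repeat triggers of 0.5% to 2% per draw, with nothing missing, would take 0.272 to about 0.32 to 0.45; proportional triggers would leave it unchanged; one-arm triggers could move it either way. The direction is not known in advance, so it should not be said that analysis 1 necessarily dilutes or exaggerates the effect.

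For analysis 4 the supported statement is that arm and visit are not among the matching variables given. If arm is in fact omitted, the pull is towards the null, and it is near nil when Table 8 is applied to the imputed values.

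Nothing here touches the primary analysis, type 1 error or event target. Severity is minor.

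**What to change.** In section 3.1.5:

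1. Define analysis 1 as relapse at the trigger date only when a repeat that Table 8 still requires is missing, and keep observed negative confirmations as non-relapse. This counts every missing repeat as positive, which should be stated.
2. If the any-trigger rule is wanted, keep it as a separately labelled stress test of the confirmation requirement.
3. State whether the one-of-two-missing rule is retained, and report it separately, so that the redefinition does not delete it unnoticed.
4. Report the numbers of missing and of negative repeats by arm.
5. For analysis 4, include treatment arm and visit in the imputation, say whether the CCS dose is baseline or current, and apply Table 8 to the imputed values.

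Items 1 to 4 cost wording and modest programming, with no extra data, because missing and negative repeats are distinguishable in the data. Item 5 may change the method. At the 4:1 female-to-male ratio in section 2.2.1, 28 per arm gives 28/5 = 5.6 men, or about 2.8 per CCS stratum if split evenly. Exact donor cells would be too thin, and a simple imputation model may be needed.
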